# 9.1. Study Endpoints:

**9.1.1. Primary Efficacy Analysis:** Clinical activity of CB-103 in combination with venetoclax will be assessed based on the overall response rate (NCCN Guidelines 2021) [30].

#### 9.1.2. Response Criteria T-ALL:

- **9.1.2.1. CR** (Complete Remission): Absolute neutrophil count >  $1.0 \times 10^9$ /L, platelets >  $100 \times 10^9$ /L, red cell transfusion independence, and bone marrow with < 5% blasts. No evidence of extramedullary disease.
- **9.1.2.2. CRi** (CR with incomplete blood count recovery): Bone marrow with < 5% blasts, with peripheral neutrophils of  $\le 1.0 \times 10^9$ /L or platelets  $\le 100 \times 10^9$ /L.
- **9.1.2.3. PR** (Partial Remission): All of the hematologic values for a CR but with a decrease of at least 50% in the percentage of blasts to 5% to 25% in the bone marrow aspirate. No evidence of extramedullary disease.
- **9.1.2.4.** Relapse: Subsequent appearance, after achievement of CR, of  $\geq$  5% blasts in the bone marrow with confirmation by flow cytometry or the development of extramedullary disease after achievement of CR.

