#### 1. OBJECTIVES

# 1.1. Primary Objectives:

- **1.1.1.** To characterize the safety and tolerability of CB-103 in combination with Venetoclax in adolescent (12 to 18 years) and adult (19 to 60 years) patients with relapsed/refractory T-cell acute lymphoblastic leukemia (T-ALL) and T-cell lymphoblastic lymphoma (T-LBL).
- **1.1.2**. To assess the efficacy of CB-103 in combination with venetoclax by the overall response rate (ORR), defined as complete remission (CR) plus CR with incomplete blood count recovery (CRi) [1] plus partial remission (PR) [2], in adolescent and adult patients with relapsed/refractory T-ALL/T-LBL.

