#### 3. STUDY POPULATION

#### 3.1. Inclusion Criteria:

**3.1.1.** Adolescent (12 to 18 years) and adult (19 to 60 years) patients who have relapsed or refractory T-cell lymphoblastic leukemia (T-ALL) or T-Cell lymphoblastic lymphoma (T-LBL) according to 2017 WHO classification [29] and NCCN v1 2021 [30]:

Patients must have  $\geq 5\%$  blasts in the bone marrow as assessed by morphology on standard bone marrow biopsy and aspirate or less than 5% blasts in the bone marrow in presence of extramedullary relapse, excluding isolated central nervous system (CNS) relapse. However, if an adequate bone marrow sample cannot be obtained, patients may be enrolled if there is unequivocal evidence of leukemia with  $\geq 5\%$  blasts in the peripheral blood.

- **3.1.2.** Patients are eligible independently of Notch pathway activation in the leukemic blasts: however, a fresh marrow/blood sample must be obtained before starting the study treatment to classify the patients as being either Notch positive or negative.
- **3.1.3.** Leukemic blasts must express of at least 2 of the following immune phenotyping: CD1a, CD2, CD3, CD4, CD5, CD7, CD8, CD34, TCR $\alpha$ B, TCR $\gamma$ S, cyCD3
- **3.1.4.** Patients have adequate performance status (ECOG ≤2) for patients ≥16 years old, Lansky score >50 for patients <16 years old.
- **3.1.5.** Patients must be 12 to 60 years of age inclusive when signing the informed consent. For patients < 18 years of age, parent or legally authorized representative (LAR) should be willing and able to give informed consent. Non-English speaking patients are eligible for whom consent process will follow institutional guidelines.
- **3.1.6.** Patients with CNS disease are eligible.
- **3.1.7.** Patients must have adequate organ function and laboratory results (obtained within 14 days of enrollment):
  - **3.1.7.1.** Direct bilirubin  $\leq 2$  x upper limit of normal (ULN).
  - **3.1.7.2.** Serum creatinine  $\leq$  1.5 x ULN; or if serum creatinine > 1.5 x ULN, then serum creatinine clearance (CrCl)  $\geq$  50 mL/min (estimated by Cockcroft-Gault formula).
  - **3.1.7.3.** Alanine aminotransferase (ALT) and/or aspartate aminotransferase (AST)  $\leq$ 3 x ULN;  $\leq$ 5 x ULN in case of suspected leukemic liver involvement

Page | 9 04/25/2024

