#### 6.2. Recommended Venetoclax Dose Modification.

Interrupt dosing, reduce number of days, or reduce dose for toxicities. Treatment modifications for venetoclax related toxicities will be performed as per the respective summaries of product characteristics (SmPC). As CB-103 and venetoclax do not have overlapping toxicity, dose modification of CB-103 is independent of venetoclax dose modification: treatment modifications for CB-103 related are described in **Section 6.1.** 

See the following **Tables 14a and 14b** for dose modifications for hematologic and other toxicities related to **venetoclax**. For patients who have had a dosing interruption greater than 1 week reassess for risk of TLS to determine if reinitiation with a reduced dose is necessary.

Table 14a: Recommended Dose Modifications of Venetoclax for Toxicitiesa

Event	Occurence	Action
	•	Tumor Lysis Syndrome
Blood chemistry		Withhold the next day's dose. If resolved within 24 to 48 hours of last dose, resume at the same dose.
changes or symptoms	Any	For any blood chemistry changes requiring more than 48 hours to resolve, resume at a reduced dose.
suggestive of TLS		For any events of clinical TLS b , resume at a reduced dose following resolution.
		Non-Hematologic Toxicities
Grade 3 or 4 non-		Interrupt venetoclax. Once the toxicity has resolved to Grade 1 or baseline level, VENCLEXTA therapy may be resumed at the same dose. No dose modification is required. Consider decreasing treatment days.
hematologic toxicities	2nd and subsequent occurrences	Interrupt venetoclax. Follow dose reduction guidelines in Table 14b when resuming treatment with Venetoclax after resolution. Consider decreasing treatment days. A larger dose reduction may occur at the discretion of the physician.
		Hematologic Toxicities
Grade 3 or 4 neutropenia with infection or fever; or	1st occurrence	Interrupt venetoclax. To reduce the infection risks associated with neutropenia, granulocyte-colony stimulating factor (G-CSF) may be administered with Venetoclax if clinically indicated. Once the toxicity has resolved to Grade 1 or baseline level, Venetoclax therapy may be resumed at the same dose. Consider decreasing treatment days.

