For any significant abnormalities seen at the eye examination, all assessed parameters and findings should be documented in the respective eCRF pages and source documents.

- **8.5. Pregnancy tests and assessment of fertility**: Only female patients of childbearing potential must undergo serum and urine pregnancy tests
- **8.6. Disease assessment**: Disease assessment by bone marrow samples (aspirate and/or biopsy), cytogenetics and flow cytometry is done at baseline screening and at completion of each treatment cycle. A bone marrow biopsy and/or aspirate will be obtained to assess bone marrow cellularity and to determine the percentage of leukemic blasts, including assessment of minimal residual disease (MRD) to confirm remission status.

At the baseline assessment, bone marrow biopsy and/or aspirate is within 3 weeks and no less than 1 day before the first drug dose. Then on each cycle, patients are assessed for disease response by bone marrow biopsy and/or aspirate on day 28. If the blasts in bone marrow are <5% but marrow is hypocellular (cellularity  $\leq$ 15%) on day 28 ( $\pm$ 3 days), then a repeat bone marrow biopsy and/or aspirate is obtained 1 week later to assess response; if residual leukemia is present, repeated bone marrow biopsy and/or aspirate will be obtained as medically indicated.

Only for patients with extramedullary disease or as clinically indicated a PET-CT will be performed at baseline and if positive, also at end of the induction and of the reinduction cycles, and thereafter as clinically indicated. A time window of  $\pm$  3 days is allowed for the tumor assessments. A wider time window is allowed only at baseline; however, assessments should be performed as close as possible to the 1st drug administration and if feasible, not later than 3 weeks prior to the 1st drug administration

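### CRi counts toward the primary ORR but omits the no-extramedullary-disease condition that CR and PR carry, and no rule says how the marrow and Lugano categories combine.

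*Combined protocol and SAP*

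**What the plan says.** **Endpoint.** Section 1.1.2 defines ORR as CR "plus CR with incomplete blood count recovery (CRi") plus PR. Section 12 uses the same three categories, assessed after the first two cycles, as the primary efficacy endpoint. Section 9.1.1 says activity is "assessed based on the overall response rate (NCCN Guidelines 2021").

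**Response categories (9.1.2).**
- CR: recovered counts, red cell transfusion independence, under 5% marrow blasts, and no extramedullary disease.
- CRi: "Bone marrow with < 5% blasts, with peripheral neutrophils of" at or below 1.0 × 10⁹/L, or platelets at or below 100 × 10⁹/L. Nothing is said about extramedullary disease.
- PR: a final blast count between 5% and 25%, extramedullary disease again excluded, and otherwise "All of the hematologic values for a CR but with a decrease of at least 50% in the percentage of blasts".

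**Who is enrolled.** Section 3.1.1 admits patients with at least 5% marrow blasts, and also those with "less than 5% blasts in the bone marrow in presence of extramedullary relapse, excluding isolated central nervous system (CNS) relapse". Section 3.1.7 opens "Patients must have adequate organ function and laboratory results (obtained within 14 days of enrollment") and then lists bilirubin, creatinine and transaminase limits. It lists no neutrophil or platelet minimum.

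**Imaging.** Section 8.6 covers scans where there is disease outside the marrow: "a PET-CT will be performed at baseline and if positive, also at end of the induction and of the reinduction cycles". Section 9.1.3, headed as additional criteria for T-LBL, has the investigator determine radiographic response by Lugano (Appendix 2).

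**Decision rule.** Table 18 has looks at 10, 20 and 30 patients and is stated to be non-binding. At 30 patients, acceptability needs more than 5 responses and fewer than 6 toxicities.

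**The concern.** A patient who enters with extramedullary relapse and under 5% marrow blasts already meets the marrow part of CRi. If neutrophils or platelets are low at the assessment, the CRi wording is met even though the active extramedullary disease has not changed. If counts are low at entry, it is met before the first dose.

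There is a second gap. Section 9.1.3 gives patients with extramedullary disease a Lugano category, but the plan does not say how that category and the 9.1.2 category become the single response that enters ORR. Two assessors who both follow the text can score the same patient differently.

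The primary endpoint is therefore undefined for a group that the trial deliberately enrols. With 30 patients, six responses satisfy the efficacy criterion, so one or two such patients can decide the conclusion when the count lies near a boundary.

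**Working it through.** **1. The categories side by side.** Take a patient with baseline extramedullary disease, under 5% marrow blasts throughout, and active extramedullary disease at the end of cycle 2.

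| Status at assessment | 9.1.2 as written | Lugano (Appendix 2) |
|---|---|---|
| Active disease unchanged, counts recovered | Not CR or PR (extramedullary disease present) | Stable disease / no response |
| Active disease unchanged, counts low | **CRi, counted in ORR** | Stable disease / no response |
| Uptake reduced, PET score 4–5, counts recovered | Not CR or PR (extramedullary disease present; blasts not 5–25%) | Partial |
| Uptake reduced, PET score 4–5, counts low | **CRi, counted in ORR** | Partial |
| Residual mass, PET score 1–3 | Depends on how 'no evidence' is read | Complete |

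Rows 1 and 2 differ only in blood counts, and it is the patient with the worse counts who is scored a responder. Row 3 shows the opposite error: a Lugano partial response with a clear marrow has no responding category in 9.1.2. Row 5 is a genuine Lugano complete response and is not part of the concern.

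**2. Reproducing the plan's figures.** Inputs from Section 12: looks at 10/20/30; stop if responses ≤ 0/2/5 or toxicities ≥ 3/5/6; multinomial joint outcomes. From λ = 0.57, α = 0.86 and prior marginals Beta(0.15, 0.85) and Beta(0.20, 0.80), the Table 18 boundaries reproduce exactly. Exact enumeration then gives, for claiming acceptability:

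| Table 19 scenario | Stated | Exact |
|---|---|---|
| 6 (0.15, 0.20, 0.05) | 8.34% | 8.17% |
| 3 (0.30, 0.10, 0.05) | 77.76% | 78.46% |
| 4 (0.15, 0.10, 0.05) | 20.83% | 21.03% |
| 7 (0.20, 0.10, 0.05) | 45.19% | 45.28% |

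All ten scenarios agree within 0.70 percentage points. Scenarios 4 and 7 differ only in the response rate, so the plan's own table shows how steeply the claim depends on it.

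**3. Sensitivity to mis-scored CRi.** Let g be the share of all patients who are non-responders scored CRi, with the same toxicity rate as everyone else. The documents give no value for g. Then

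- p_eff = 0.15 + g
- p_efftox = 0.05 + g × p_tox

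For example, g = 1/30 with p_tox = 0.20 gives p_eff = 0.1833 and p_efftox = 0.05 + 0.0067 = 0.0567. Chance of claiming acceptability if Table 18 is followed:

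| g | p_eff | p_tox 0.20 | p_tox 0.10 |
|---|---|---|---|
| 0 | 0.150 | 8.2% | 21.0% |
| 1/300 | 0.153 | 8.8% | 22.5% |
| 1/30 | 0.183 | 14.7% | 36.9% |
| 5% | 0.200 | 18.1% | 45.0% |

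At p_tox 0.20 the probability reaches 10% at g of about 1.0% and doubles at about 4.1%. Giving the mis-scored group the non-responders' own toxicity rate, (0.20 − 0.05)/0.85 = 17.6%, changes the 5% entry only from 18.12% to 18.22%.

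**The case against.** The strongest reply is that no assessor would score this way. CRi is by name a CR with incomplete count recovery, and CR, defined immediately above it, excludes extramedullary disease. Section 9.1.3 sends patients with extramedullary disease to Lugano, where a persisting active, non-progressing lesion is stable disease. Section 8.6 puts PET-CT inside the disease assessment. This is persuasive about intent, and a drafting omission is the likely explanation. But the operative definition stands without the condition, 9.1.3 is headed as additional and states no precedence, and nothing says that Lugano overrides 9.1.2. The cited NCCN text may settle the matter, but it is not available here.

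Three further objections stand and limit the point:
- **Not every residual mass.** Appendix 2 counts PET score 1–3 as complete with or without a residual mass. Only active extramedullary disease is at issue.
- **Weak supporting text.** Section 12 lists radiographic response among other measures of response, but that list also contains CR, CRi and PR, so it does not show that imaging is outside ORR. Table 14a's rows on neutropenia concern dose interruption and say nothing about counts at the response assessment. Neither is relied on here.
- **Assumed size.** The shares are hypothetical, and scenarios 4 and 7 show sensitivity to the response rate in general, not to CRi.

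A reader might infer that the stated 8.3% type I error is wrong. The documents do not support that: the figure reproduces, and it is conditional on a response rate of 0.15 for the endpoint as scored.

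**Conclusion.** The point holds as a defect in the written definition. CRi lacks a condition that both neighbouring categories carry, the trial enrols patients to whom this matters, and the plan does not say which category enters ORR when 9.1.2 and Lugano disagree. The error can run either way: CRi can count a non-response, and 9.1.2.3 can exclude a Lugano partial response.

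The size is conditional. It assumes that Table 18 is followed although non-binding, that some patients really are scored this way, and that the 0.15 benchmark does not itself count such patients. The text available does not say how 0.15 was derived; if it was scored the same way, there is no inflation. The documents do not support concluding that the plan intends to count non-responders, or that any have been counted.

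**What to change.** 1. Add the CR condition on extramedullary disease to 9.1.2.2 for the purpose of ORR and Table 18.
2. State in 9.1.3 and Section 12 which single category (9.1.2, Lugano or a stated combination) enters ORR for patients with baseline extramedullary disease. Reconcile 9.1.2.3 with it, and confirm that 0.15 and 0.30 refer to the endpoint so defined.
3. Apply the rule to patients already assessed. Because the trial is open-label and their outcomes are known, report ORR under both the current protocol wording and the amended wording.
4. Sections 4.2.3 and 4.3.2 use the CR/CRi label to decide treatment continuation, so they must be reconciled with the edited definition. No clinical rule is proposed here.

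The cost is text edits and re-scoring. No new tests are needed, because Section 8.6 already schedules PET-CT at baseline and, if positive, after induction and reinduction. The counted ORR may change in either direction.

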### 9.1.3. Additional Response Criteria for T-LBL:

In patients with extramedullary disase, radiographic tumor response assessments will be based on CT/MRI/PET-CT scans throughout the study and response determined by Investigator per the revised recommendations for response assessment of NHL per "The Lugano Classification", reported in **Appendix 2** [31].

**Measured dominant lesions**: Up to six of the largest dominant nodes, nodal masses, and extranodal lesions selected to be clearly measurable in two diameters. Nodes should preferably be from disparate regions of the body and should include, where applicable, mediastinal and retroperitoneal areas. Non-nodal lesions include those in solid organs (eg, liver, spleen, kidneys, lungs), GI involvement, cutaneous lesions, or those noted on palpation.

**Nonmeasured lesions**: Any disease not selected as measured, dominant disease and truly assessable disease should be considered not measured. These sites include any nodes, nodal masses, and extranodal sites not selected as dominant or measurable or that do not meet the requirements for measurability but are still considered abnormal, as well as truly assessable disease, which is any site of suspected disease that would be difficult to follow quantitatively with measurement, including pleural effusions, ascites, bone lesions, leptomeningeal disease, abdominal masses, and other lesions that cannot be confirmed and followed by imaging.

Protocol 2021-0547 4/25/2024

#### 9.1.4. Response Criteria for CNS Disease:

**9.1.4.1. CNS remission**: achievement of CNS-1 status in a patient with CNS-2 or CNS-3 status at diagnosis.

**9.1.4.2. CNS relapse**: new development of CNS-3 status or clinical signs of CNS leukemia New development of CNS-2 status on 2 consecutive lumbar punctures (between 2–4 weeks apart) with confirmation by immunophenotyping or other molecular testing methods.

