- **3.2.10.** Patients with unresolved nausea, vomiting, or diarrhea of CTCAE version 5.0, grade > 1 from prior therapy.
- **3.2.11.** Patients with impairment of GI function or GI disease presence that may significantly alter the absorption of CB-103 (e.g., ulcerative diseases, uncontrolled nausea, vomiting, diarrhea, malabsorption syndrome, or small bowel resection).
- **3.2.12.** Have current or recurrent (within 3 months) gastrointestinal disease, have conditions requiring chronic systemic glucocorticoid use, have active graft versus host disease, or have a second primary or prior malignancy that would affect the interpretation of study results. Low doses of corticosteroids (10 mg prednisone equivalent a day) are permitted.
- **3.2.13.** Prior chemotherapy/radiotherapy/investigational therapy within 2 weeks before the start of study drugs with the following exceptions:
  - **3.2.13.1.** Up to 5 days of glucocorticoids (10 mg of dexamethasone or equivalent/day) in combination with up to 3 doses of cyclophosphamide (200 mg/m $^2$ /day) are allowed as standard pre-phase treatment up to 1 day before start of study treatment. Cytarabine up to 2gm/m $^2$  are also allowed as standard pre-phase treatment up to 1 day before start of study treatment.
  - **3.2.13.2.** Mercaptopurine may be dosed up to 5 days prior to first dose of CB103
  - **3.2.13.3.** Vinca alkaloids may be dosed up to 5 days prior to first dose of CB103
  - **3.2.13.4.** Prophylactic intrathecal (IT) chemotherapy may be dosed up to 1 day prior to first dose of CB103
- **3.2.14.** Females who are pregnant or lactating.

Page | 11 04/25/2024

- **3.2.15.** Male or female subjects of childbearing potential, unwilling to use an approved, effective means of contraception in accordance with institution's standards.
- **3.2.16.** Other severe, uncontrolled acute or chronic medical or psychiatric condition or laboratory abnormality that in the opinion of the Investigator may increase the risk associated with study participation or investigational product administration or may interfere with the interpretation of study results and/or would make the patient inappropriate for enrollment into this study.
- **3.2.17.** Patients who are unable or unwilling to comply with all study requirements for clinical visits, examinations, tests, and procedures.
- **3.2.18.** Patients must be excluded if they are currently enrolled in another ongoing clinical trial with anti-cancer investigational products

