#### 4. TREATMENT PLAN

# 4.1. Study Design

[figure not shown]
This study is designed as a phase II open-label single-arm clinical trial to evaluate the efficacy and safety of CB-103 in combination with venetoclax in adolescent and adult patients with T-ALL/T-LBL with relapsed or refractory disease.

Patients are eligible independently of Notch pathway activation in the leukemic blasts: however, a fresh marrow/blood sample must be obtained before starting the study treatment to classify the patients as being either Notch positive or negative. Notch pathway activation is defined presence of Notch1 gain-of-function (GOF) mutations, or FBXW7 loss-of-function (LOF) mutations, or Notch3 GOF mutations or Notch1 translocations detected by Next Generation Sequencing (NGS). Details on molecular alterations as signs of Notch pathway activation and the specific test method can be found in the laboratory manual.

The study consists of three periods (Figure 2):

- Screening period (including baseline assessments)
- Treatment period (including an End-of-Treatment [EOT] visit)
- Survival follow-up period

Figure 2: Study design schema

A cycle of treatment is defined as 28 days of treatment with CB-103 and Venetoclax.

Page | 12 04/25/2024

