- **8.1. Medical History and Demographic Data**: Medical history includes clinically significant diseases, surgeries, reproductive status, smoking history, use of alcohol and drugs of abuse, all medications (e.g., prescription drugs, over the counter drugs, herbal or homeopathic remedies, nutritional supplements) and physical/occupational/exercise. Demographic data will include year of birth, sex and self reported race/ethnicity (collecting this information is essential in order to be able to evaluate the results of this study, for example, in the case of PK outliers or important between-patient differences in terms of treatment effect). Evaluation of the inclusion and exclusion criteria will be performed at the screening visit.
- **8.2. Disease History**: The patients' disease history from the time of diagnosis (including any biomarker information and details regarding anti-neoplastic treatments they have received in the past) will be collected at screening. The exact parameters to be collected will be outlined on the respective screening eCRF pages. Disease history will be taken at the screening visit.
- **8.3. ECOG performance status**: Performance status will be measured using the ECOG performance status scale (**Table 15a**). Patient's performance status should preferentially be assessed by the same person throughout the study.

**Table 15a**: ECOG performance status grading

Grade	Performance Status
0	Fully active, able to carry on all pre-disease performance without restriction
1	Restricted in physically strenuous activity but ambulatory and able to carry out workof a light or sedentary nature, i.e., light housework, office work
2	Ambulatory and capable of all self-care but unable to carry out any work activities. Upand about more than 50% of waking hours

Protocol 2021-0547 4/25/2024

3	Capable of only limited self-care, confined to bed or chair more than 50% of wakinghours
4	Completely disabled. Cannot carry on any self-care. Totally confined to bed or chair
5	Dead

Source: http://www.ecog.org/general/perf stat.html

Lansky scale may be used with adolescent of age  $\leq$  16 years (Table 14b). It is rated by parents based on their child's activity over the past week. Parents fill out the assessment based on the directions on the form, and the form is readministered over time to assess for changes in performance status.

Table 15b: Lansky performance status grading

Rating	Description
100	Fully active, normal

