- 14. Lumbar puncture (T-ALL/T-LBL) for prophylactic intrathecal therapy: if prophylactic intrathecal therapy is foreseen by the treating physician, a lumbar puncture may be performed up to 3 days before the first dose of CB-103, and may be repeated at the discretion of the treating physician at the end of the first cycle and at the end of any subsequent cycles on or around day 28. If clinically feasible, one additional sample will be collected to determine the exposure of CB-103 in the CSF (this measurement will be done by a designated laboratory under Cellestia's responsibility).
- 15. For patients with PR or stable disease (SD) after the induction cycle(s) who may receive add-on selective therapy chosen by the investigator on the basis of the ongoing biomarker expression of the disease while continuing the treatment with the combination of CB-103 and venetoclax, the add-on therapy will be reported in details on the CRF.
- 16. EoT visit is to be done 5 days after the last dose of any study treatment, unless the patient starts any subsequent antitumor therapy (in which case the EoT visit should be performed before the start of the new therapy, whenever possible).
- 17 First follow-up visit will be 26 days after EoT (± 5 days), and every three months (± 14 days) thereafter, until EoS (i.e., death, patient's refusal, lost to follow-up) or study termination, whichever occurs first. Survival status and information on posterior antitumor therapies will be collected, telephone contact being acceptable.
- 18. If patient discontinued treatment without progression, tumor assessment will be done until progression or start of new antitumor treatment.
- 19. In case of relevant related toxicities (i.e., Grade>1), every 4 weeks until resolution or stabilization: information collected by telephone contact is acceptable.
- 20. Hepatitis B, C infection, and HIV will be obtained within 21 days of start of treatment.

Protocol 2021-0547 4/25/2024

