25/30     0.83 (0.66, 0.93)       26/30     0.87 (0.7, 0.95)       27/30     0.9 (0.74, 0.97)       28/30     0.93 (0.78, 0.99)       29/30     0.97 (0.82, 1)	23/30	0.77 (0.59, 0.88)
26/30     0.87 (0.7, 0.95)       27/30     0.9 (0.74, 0.97)       28/30     0.93 (0.78, 0.99)       29/30     0.97 (0.82, 1)	24/30	0.8 (0.62, 0.91)
27/30     0.9 (0.74, 0.97)       28/30     0.93 (0.78, 0.99)       29/30     0.97 (0.82, 1)	25/30	0.83 (0.66, 0.93)
28/30 0.93 (0.78, 0.99) 29/30 0.97 (0.82, 1)	26/30	0.87 (0.7, 0.95)
29/30 0.97 (0.82, 1)	27/30	0.9 (0.74, 0.97)
	28/30	0.93 (0.78, 0.99)
30/30 1 (0.87, 1)	29/30	0.97 (0.82, 1)
	30/30	1 (0.87, 1)

In secondary analysis, ORR will be summarized separately by Notch status as proportions with corresponding 95% Agresti-Coull confidence intervals. The difference in ORR between Notch groups will be assessed by Fisher's exact test.

Other measures of response (CR, Cri, PR, relapse, radiographic tumor response, CNS remission, CNS relapse) and minimal residual disease (MRD) will be summarized as proportions with corresponding 95% Agresti-Coull confidence intervals.

Duration of Response (DoR), Overall Survival (OS), and event-free Survival (EFS) will be summarized using Kaplan-Meier methods.

In exploratory analyses, correlations between ORR and pharmacokinetic and pharmacodynamics markers will be summarized. Rates of patients transitioning to Hematopoietic stem cell transplant (HSCT) will be summarized. Endpoints may be further summarized separately by Notch status.

Additional statistical methods may be used.

The Investigator is responsible for completing an efficacy/safety summary reports and submitting it to the IND Office Medical Affairs and Safety Group, for review and approval.

This should be submitted after the first 10 evaluable patients complete 1 cycle of study treatment, and every 10 evaluable patients, thereafter. Efficacy summary will be submitted for every 10 evaluable patients after they complete 2 cycles of therapy.

Page | 52 04/25/2024

A copy of the safety summary report should be placed in the Investigator's Regulatory Binder under "sponsor correspondence".

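### CNS remission is referenced to CNS status at diagnosis in a relapsed/refractory trial, so a patient whose CNS disease first appears at relapse cannot count as a remission

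*Combined protocol and SAP*

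**What the plan says.** Section 9.1.4.1 defines CNS remission as "achievement of CNS-1 status in a patient with CNS-2 or CNS-3 status at diagnosis". The trial enrols "adolescent and adult patients with T-ALL/T-LBL with relapsed or refractory disease" (Section 4.1). Inclusion criterion 3.1.6 states "Patients with CNS disease are eligible". Criterion 3.1.1 admits low-marrow-blast patients with extramedullary relapse, "excluding isolated central nervous system (CNS) relapse", so CNS disease combined with marrow or other extramedullary relapse is allowed.

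Section 12 places CNS remission among the other measures of response: "radiographic tumor response, CNS remission, CNS relapse) and minimal residual disease (MRD) will be summarized as proportions", with 95% Agresti-Coull intervals. It states no denominator for it.

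On CNS status at entry, Table 16 marks a screening lumbar puncture. Footnote 14 makes it conditional on planned prophylactic intrathecal therapy: "a lumbar puncture may be performed up to 3 days before the first dose of CB-103". Exclusion 3.2.13.4 adds that "Prophylactic intrathecal (IT) chemotherapy may be dosed up to 1 day prior to first dose of CB103".

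**The concern.** A definition anchored at diagnosis suits a newly diagnosed population, where diagnosis and baseline coincide. Here earlier treatment lies between them, and CNS status can change in either direction.

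Two kinds of patient are then at risk of misclassification. One is CNS-1 at diagnosis, enters with CNS-2/3 and clears on study. This patient lacks the required status at diagnosis and cannot be counted. The other is CNS-2/3 at diagnosis, is cleared by earlier therapy and enters as CNS-1. This patient may be counted although nothing changed on study.

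At stake is whether the reported proportion describes clearance of CNS disease present at the start of CB-103 plus venetoclax, or mixes that with the effect of earlier treatment. Two analysts could also reach different counts from the same data.

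**Working it through.** **What 'diagnosis' means.** No section redefines it as screening, baseline or the current relapse. Section 8.2 collects "disease history from the time of diagnosis", including past anti-neoplastic treatments, so there the word marks the start of the disease. Other measures use a study reference: EFS starts at C1D1 (Section 9.1.5), and partial metabolic response is judged against baseline (Appendix 2).

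**The plan's own interval.** Agresti-Coull: ñ = n + z², p̃ = (x + z²/2)/ñ, limits p̃ ± z√(p̃(1 − p̃)/ñ), with z = 1.96, truncated to 0 and 1. For 5/30: ñ = 33.84, p̃ = 6.92/33.84 = 0.2045, half-width 0.136, giving 0.07 to 0.34 as in Table 20. All rows of Table 20 reproduce. The plan states no figure for CNS remission itself.

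**Set-up.** Let a = patients CNS-2/3 at both diagnosis and entry; b = CNS-2/3 at diagnosis, CNS-1 at entry; c = CNS-1 at diagnosis, CNS-2/3 at entry. Let ra and rc be the numbers in a and c who clear on study.

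- Diagnosis anchor, permissive reading (being CNS-1 on study is enough): (ra + b)/(a + b)
- Diagnosis anchor, strict reading (an on-study change is required): ra/(a + b)
- Entry anchor: (ra + rc)/(a + c)

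All counts below are assumed. The denominators for the diagnosis anchor are also assumed, because Section 12 gives none.

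| a, b, c | ra, rc | Diagnosis, permissive | Diagnosis, strict | Entry |
|---|---|---|---|---|
| 3, 0, 0 | 1, 0 | 1/3 = 0.33 (0.06, 0.80) | 1/3 | 1/3 = 0.33 (0.06, 0.80) |
| 3, 1, 1 | 1, 0 | 2/4 = 0.50 (0.15, 0.85) | 1/4 | 1/4 = 0.25 (0.03, 0.71) |
| 3, 3, 3 | 1, 1 | 4/6 = 0.67 (0.30, 0.91) | 1/6 | 2/6 = 0.33 (0.09, 0.70) |
| 3, 3, 3 | 0, 0 | 3/6 = 0.50 (0.19, 0.81) | 0/6 | 0/6 = 0 (0, 0.44) |

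Example for 4/6: ñ = 6 + 3.84 = 9.84, p̃ = (4 + 1.92)/9.84 = 0.602, half-width 1.96 × √(0.602 × 0.398/9.84) = 0.306, giving 0.30 to 0.91.

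**Reading the table.** With b = c = 0 the rules agree. Under the permissive reading, the b patients inflate the numerator even when nobody clears. Under the strict reading that inflation disappears, but the third row still loses the one clearance in group c: one of two on-study clearances is counted.

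**Denominator of 30.** If all 30 patients were the denominator, the third row would be 4/30 (0.05, 0.30) against 2/30 (0.01, 0.22), and the fourth 3/30 (0.03, 0.26) against 0/30 (0, 0.13), using the Table 20 intervals.

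**The case against.** The strongest reply is that the text can be read more kindly. 'Achievement' may imply a change on study, so a patient already CNS-1 at entry would not qualify. 'Diagnosis' may mean diagnosis of the current relapse; Section 7.1 itself speaks of CNS involvement diagnosed after enrolment. The first argument stands in part: over-counting depends on the reading and is not certain. It does not help the patient whose CNS disease appears only at relapse, who fails the condition however 'achievement' is read. The second is possible, but nothing in 9.1.4.1 says so, and Section 8.2 points the other way. If study entry was meant, the words still need changing.

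The reply is also right about importance. CNS remission is named in no objective in Section 1 and in neither endpoint list in 9.1.5 and 9.1.6. With at most 30 patients and isolated CNS relapse excluded, few patients may be affected, and the intervals overlap heavily in the milder case.

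A reader might go further and infer that every patient cleared before enrolment counts as a remission, that the measure says nothing about CNS disease on study, or that a very large gap should be expected. The documents support none of these. The first depends on the reading. The second overlooks patients positive at both times, who are classified correctly. The third needs CNS counts that the documents do not give.

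**Conclusion.** The reference time point in 9.1.4.1 does not fit this population and should be corrected. One error is firm if diagnosis means original diagnosis: CNS-2/3 disease present only at entry and cleared on study cannot count. The other, counting patients cleared earlier, is possible but not established.

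The size rests wholly on assumed counts. Under the permissive reading it runs from no difference, through 0.50 against 0.25, to 0.67 against 0.33, or 0.50 against 0 when nobody clears on study. Under the strict reading the effect is limited to missed clearances.

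A reader might suspect that the primary result is touched. It is not. ORR is CR plus CRi plus PR. CR asks for no extramedullary disease at assessment but does not use the CNS remission rule, and the BOP2 boundaries and Tables 18 and 19 do not involve it. The consequence is confined to one descriptive proportion.

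**What to change.** In 9.1.4.1, replace the reference to diagnosis with CNS status at study baseline, defined as the last CNS assessment before the first dose. In Section 12:

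- set the denominator as patients with documented CNS-2 or CNS-3 at that baseline;
- list patients without a pre-dose CSF as not evaluable for CNS remission, since footnote 14 of Table 16 makes the puncture optional and a change of wording alone would leave their baseline undefined;
- label the result as response on study drugs plus intrathecal therapy, which Section 5.3 provides as standard of care.

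The cost is a few lines of text and a smaller denominator, hence wider intervals. One limit remains: because prophylactic intrathecal chemotherapy is allowed until the day before the first dose, the last pre-dose CSF may follow such treatment. The label should make clear that clearance is not attributed to the study drugs alone.
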